### 2.5.5 Pharmacokinetic Measurements

Blood samples (2 ml) for the determination of plasma AZD6244, N-desmethyl AZD6244 and AZD6244 Amide determination will be collected from patients in a comprehensive PK sampling schedule. Blood will be immediately placed on ice and the specimen transported to the laboratory of [name] for processing and storage. Analysis of plasma samples for the determination of AZD6244, N-desmethyl AZD6244 and AZD6244 Amide concentrations will be the responsibility of the Clinical Pharmacology

& DMPK(Drug Metabolism and Pharmacokinetics) Department, Alderley Park, AstraZeneca, UK. Specimens will be shipped in batches from [name] laboratory to Astra Zeneca's contract laboratory for analysis.

For once daily dosing (dose level -1)

- Day 4 or 5 (AZD6244 alone): Pre-dose (within 10 minutes of dosing), 30 minutes, 1 hour, 1 hour 30 minutes, 2, 4, 8, 12 and 24 hours post-dose (24 hour sample is pre- the next day's dose).
- Day 11 or 12 (AZD6244 + capecitabine + radiotherapy): Pre-dose (within 10 minutes of dosing), 30 minutes, 1 hour, 1 hour 30 minutes, 2, 4, 8, 12 and 24 hours post-dose (24 hour sample is pre- the next day's dose).

For twice daily dosing (dose levels 1 and 2):

- Day 4 or 5 (AZD6244 alone): Pre-dose (within 10 minutes of dosing), 30 minutes, 1 hour, 1 hour 30 minutes, 2, 4, 8 and 12 hours post-dose (12 hour sample is pre- the next day's dose).
- Day 11 or 12 (AZD6244 + capecitabine + radiotherapy): Pre-dose (within 10 minutes of dosing), 30 minutes, 1 hour, 1 hour 30 minutes, 2, 4, 8 and 12 hours post-dose (12 hour sample is pre- the next day's dose).

The actual sample time and date of all PK samples will be recorded.

### 3. PATIENT SELECTION

#### 3.1 Eligibility Criteria

3.1.1 Patients must have histologically or cytologically confirmed locally advanced, non-metastatic adenocarcinoma of the rectum (clinical stage T3 anyN, T4 anyN, or AnyT N+).

3.1.2 Patients with recurrent adenocarcinoma of the rectum with no clinically evident distant disease will be eligible if they are deemed to have pelvic nodal metastases or disease extending through the muscularis of the rectum. These patients should be evaluated by a Radiation Oncologist, Medical Oncologist and Surgeon prior to enrolling on study to confirm anticipated resectability. These patients should not have received prior radiotherapy for management of their rectal cancer.

3.1.3 Age  $\geq$ 18 years.

3.1.4 ECOG performance status  $\leq$ 1 (Karnofsky  $\geq$ 70%, see Appendix A).

3.1.5 Patients must have normal organ and marrow function as defined below:

- leukocytes  $\geq$ 3,000/mcL
- absolute neutrophil count  $\geq$ 1,500/mcL
- platelets:  $\geq$ 100,000/mcL

- total bilirubin: within normal institutional limits except for patients with Gilbert's who must have a direct bilirubin < 1.0 mg/dL
- AST(SGOT)/ALT(SGPT)  $\leq 2.5$  X institutional upper limit of normal
- creatinine within normal institutional limits  
OR
- creatinine clearance  $\geq 60$  mL/min/1.73 m^2 for patients with creatinine levels above institutional normal.

3.1.6 Women of child-bearing potential and men must agree to use adequate contraception (hormonal or barrier method of birth control; abstinence) prior to study entry, for the duration of study participation, and for six months after the completion of radiation. Women of child-bearing potential must have a negative pregnancy test prior to entry. Should a woman become pregnant or suspect she is pregnant while participating in this study, she should inform her treating physician immediately. Adequate contraception for male patients should be used for 6 months after irradiation.

3.1.7 Ability to understand and the willingness to sign a written informed consent document.

3.1.8 Willingness to sign a release of medical records pertaining to previous and future treatment for rectal cancer.

### 3.2 Exclusion Criteria

3.2.1 Chemotherapy or radiotherapy within 4 weeks (6 weeks for nitrosoureas or mitomycin C) prior to entering the study or lack of recovery from adverse events due to agents administered more than 4 weeks earlier.

3.2.2 Patients may not be receiving any other investigational agents.

3.2.3 History of allergic reactions attributed to compounds of similar chemical or biologic composition to AZD6244 or other agents used in study.

3.2.4 Previous MEK inhibitor use.

3.2.5 Contraindications to radiotherapy to the pelvis such as inflammatory bowel disease or known genetic sensitivity to ionizing radiation such as ataxia telangiectasia.

3.2.6 Uncontrolled intercurrent illness including, but not limited to, ongoing or active infection, symptomatic congestive heart failure, unstable angina pectoris, cardiac arrhythmia, or psychiatric illness/social situations that would limit compliance with study requirements.

- 3.2.7 Patients with QTc interval >470 msec or other factors that increase the risk of QT prolongation or arrhythmic events (*e.g.*, heart failure, uncorrectable hypokalemia, family history of long QT interval syndrome) including heart failure that meets New York Heart Association (NYHA) class III and IV definitions (see Appendix B) are excluded.
- 3.2.8 Required use of a concomitant medication that can prolong the QT interval. See Appendix C for a table of medications with the potential to prolong the QTc interval. A comprehensive list of agents with the potential to cause QTc prolongation can be found at <http://www.arizonacert.org/medical-pros/drug-lists/drug-lists.htm>.
- 3.2.9 Refractory nausea and vomiting, chronic gastrointestinal diseases (*e.g.* inflammatory bowel disease), or significant bowel resection that would preclude adequate absorption.
- 3.2.10 HIV-positive patients on combination antiretroviral therapy.
- 3.2.11 Known dihydropyrimidine dehydrogenase deficiency.
- 3.2.12 History of prior radiation to the pelvis
- 3.2.13 For patients with newly diagnosed rectal cancer, prior therapy for adenocarcinoma of the rectum with the exception of diverting colostomy if required to relieve obstruction (including chemotherapy).
- 3.2.14. Patients with recurrent rectal cancer may not have undergone prior radiotherapy for rectal adenocarcinoma or have received therapy for the recurrence with the exception of diverting colostomy if required to relieve obstruction.
- 3.2.15 History of myocardial infarction within the past 6 months or history of ventricular arrhythmia
- 3.2.16 Uncontrolled hypertension
- 3.2.17 Pregnant or lactating females are excluded

### 3.3 **Research Eligibility Evaluation**

All referred patients who meet the eligibility criteria will be evaluated in the Radiation Oncology Clinic at the National Cancer Institute. All screening studies will be performed within 14 days of protocol enrollment unless otherwise stated.

3.3.1 Clinical evaluation including documentation of performance status, medications and prior history of radiation, including smoking history

- EKG for determination of QTc
- Total colonoscopy within 8 weeks of onset of study when possible. This may be performed at an outside institution as long as the report is available for

- review.
- Pulse oximetry
- Echocardiogram or MUGA

### 3.3.2 Radiographic studies:

- CT (chest, abdomen and pelvis) to confirm the absence of metastases will be reviewed to confirm the presence of resectable disease within 4 weeks of onset of study (outside studies may be used if acquired in the appropriate timeframe).
- Transrectal ultrasound or MRI of the pelvis to stage primary or locally recurrent rectal tumor within 4 weeks of onset of study (outside studies may be used if acquired in the appropriate timeframe).

### 3.3.3 Laboratory studies:

- Serum creatinine, Serum hepatic panel, complete blood count with differential, APTT, PT. Urine pregnancy test for women of childbearing potential, serum CEA level

### 3.3.4 Pathologic assessment:

- A copy of path report along with slides and blocks of biopsy material for review by NCI Surgical Pathology.

### 3.3.5 Surgical consultation:

- NIH surgical consultation will be obtained for all patients.

## **3.4 Registration Procedures**

Authorized staff must register an eligible candidate with the NCI Central Registration Office (CRO) within 24 hours of signing consent. A registration Eligibility Checklist from the Web site (<http://camp.nci.nih.gov/ccr/welcome.htm>) must be completed and faxed to [contact]. After confirmation of eligibility at Central Registration Office, CRO staff will call pharmacy to advise them of the acceptance of the patient on the protocol prior to the release of any investigational agents. Verification of Registration will be forwarded electronically via e-mail. Please note that it is very important for all registrars to acquire encrypted e-mail from the NIH Help Desk since the verification of registration includes patient information. A recorder is available during non-working hours.

## **4. TREATMENT PLAN**

### **4.1 Protocol Therapy Administration**

#### 4.1.1 AZD6244 administration

Treatment will be administered on an outpatient basis. Reported adverse events and potential risks for AZD6244, radiation, and Capecitabine are described in Section 6. Appropriate dose modifications for AZD6244 and Capecitabine are described in Section 5. No investigational or commercial agents or therapies other than those described below may be administered with the intent to treat the patient's malignancy.

Dose Escalation Schedule			
Dose Level	Dose		
	AZD6244	Capecitabine	Radiation*
Level -1	50 mg PO QD Weeks 1-7	825 mg/m  PO every 12 hours Weeks 2-7	5040 cGy Weeks 2-7
Level 1	50 mg PO BID Weeks 1-7	825 mg/m  PO e every 12 hours Weeks 2-7	5040 cGy Weeks 2-7
Level 2	75 mg PO BID Weeks 1-7	825 mg/m  PO every 12 hours Weeks 2-7	5040 cGy Weeks 2-7

\* An additional 360 cGy may be delivered for fixed T4 tumors for a total dose of 5400 cGy

Dose-escalation of AZD6244 will begin at dose level 1, 50 mg PO BID delivered continuously, 7 days per week beginning one week prior to the initiation of chemoradiotherapy and continuing until the last day of chemoradiotherapy. Dose level -1 will only be delivered if Dose Level 1 is considered to be not tolerated due to toxicity observed in dose level 1 patients.

- Patients will be provided with a Medication Diary for AZD6244 (Appendix D), instructed in its use, and asked to bring the diary with them to each appointment.
- Take AZD6244 capsules on an empty stomach (either 1 hour before or 2 hours after meals). AZD6244 capsules should be taken with water only.
- In the event of AZD6244 de-escalation to dose level -1 (50 mg PO QD), the patient will be instructed to take AZD6244 as a morning dose.
- Follow up for certain adverse events (AEs) should be performed to better characterize the effects of AZD6244 therapy:
  - Patients experiencing **edema** should have cardiac ejection fraction (EF) measurements, electrocardiogram, serum chemistry (including electrolytes and albumin), and routine urinalysis.
  - Patients with symptoms consistent with **cardiac** impairment (*e.g.*, congestive cardiac failure, edema, or dyspnea) should have EF measurements (MUGA scan or echocardiography) and electrocardiogram at the time of the event as well as other routine investigations.
  - **Respiratory** events (including dyspnea or pulmonary edema) should be followed up with an electrocardiogram, EF measurement, and chest X-ray.
  - Oxygen saturation will be measured at baseline and again following any **respiratory event**.
  - Patients experiencing **visual disturbances** should undergo a complete ophthalmologic examination, including a slit lamp examination.

#### 4.1.2 Capecitabine administration

Capecitabine will be administered at a dose of 825 mg/m^2 PO every 12 hours delivered approximately two hours prior to radiotherapy and the second dose will be delivered 12 hours later. Doses will be rounded to the nearest 150 mg. Patients will begin Capecitabine dosing on the first day of radiotherapy and will continue to receive Capecitabine on days of radiotherapy (Monday through Friday) until the final day of radiotherapy. Patients will be instructed to take Capecitabine with food.

Administration with Warfarin can increase the INR beyond expected. Capecitabine should not be administered with aluminum hydroxide or magnesium hydroxide containing antacids, such as Maalox, as it may increase the plasma concentrations of capecitabine and its metabolites.

#### 4.1.3 Radiotherapy administration

##### 4.1.3.1 Modality, Fractionation, and total dose

Radiation will be delivered with external beam radiation with megavoltage radiation with beam energies of 6MV or higher. Treatment will be delivered in 1.8 Gy fractions 5 days per week with every field treated each day. The total dose to the PTV encompassing the pelvic lymph nodes and tumor will be 45 Gy in 25 fractions. A boost to the tumor will be delivered for an additional 5.4 Gy in 1.8 Gy fractions. Fixed T4 tumors may receive a boost of 9 Gy for a total dose of 54 Gy.

##### 4.1.3.2 Simulation

Patients will be simulated supine or prone as appropriate to the clinical status and staging. Simulation will be performed with a CT simulator in the Radiation Oncology Branch. Oral contrast will be delivered approximately one hour prior to simulation to allow opacification of small bowel unless contraindicated. Rectal contrast will be delivered just prior to simulation unless contraindicated. An anal marker will be used at the time of simulation.

##### 4.1.3.3 Volume definitions

Initial pelvic field: The gross tumor volume (GTV) will be defined as all gross disease evident on imaging and examination. The clinical target volume (CTV) will be defined as the combination of

- 1) the rectal GTV with a 2.5 cm craniocaudal margin and a 1.5 cm radial margin
- 2) the nodal GTV with 1.5 cm margin
- 3) the iliac vessels with 1 cm margin (including the external iliac vessels only if T4 and invading anterior structures) extending craniocaudally to the L5/S1 interspace
- 4) the presacral space from S1-S5
- 5) the mesorectal and perirectal lymphatics. The planning target volume will be defined as the CTV with a 5-7 mm margin.

Boost field: The boost field will include the gross tumor including involved lymph nodes with a 2.0 cm margin to CTV. The boost field CTV must include the sacral hollow. The PTV will be defined as CTV with 5 to 7 mm margin.

##### 4.1.3.4 Dose specification

The PTV doses should meet the following criteria:

- 1) > 93% of the PTV should receive at least 93% of the prescribed dose
- 2) < 5% of the PTV should receive more than 110% of the prescribed dose. Efforts will be made to reduce heterogeneity if possible.

#### 4.1.3.5 Normal structures

Minor modifications to normal tissue dose constraints will be made if the total tumor dose is 5400 cGy. Every effort will be made to minimize areas of non target tissue that receive target doses. Specific attention will be paid to reducing exposure to small bowel, ileocecal region, femoral neck, bladder, and anal sphincter if uninvolved. The following organs will be contoured for treatment planning purposes and will be evaluated with dose volume histograms: bladder, femoral neck and head, small bowel.

The following dose goals will apply for normal tissues:

Small bowel: No more than 180 cc above 35 Gy, No more than 100 cc above 40 Gy, No more than 65 cc above 45 Gy, No small bowel volume should receive 50 Gy

Femoral heads: No more than 40% volume above 40 Gy, No more than 25% volume above 45 Gy, No femoral head volume should receive 50 Gy

Bladder: No more than 40% volume above 40 Gy, No more than 15% volume above 45 Gy, No bladder volume should receive 50 Gy

#### 4.1.4 Surgery

Surgery is not part of this protocol. It is anticipated that at the completion of chemoradiation patients will have a four to six week recovery period and will undergo surgical resection as is the current clinical standard. Surgical specimens will be reviewed by the Surgical Pathology laboratory at NIH for examination and determination of response.

#### 4.2 **Definition of Dose-Limiting Toxicity**

- Dose-limiting toxicities will be defined as follows (during treatment and within the first three weeks after treatment):
  1. Recurring and persistent Grade 3 diarrhea despite appropriate medical therapy.
  2. ANC <500 for more than 5 days or neutropenic fever
  3. Grade 4 thrombocytopenia
  4. Recurring and persistent Grade 3 nausea/vomiting despite appropriate anti-emetic therapy
  5. Grade 4 dermatitis acneiform rash
  6. Grade 4 fatigue
  7. All other non-hematologic toxicities of grade 3 or higher except electrolyte abnormalities that are correctable
  8. Delays in radiation treatment due to toxicity of more than 2 weeks (cumulative duration over the course of the entire treatment).
- Management and dose modifications associated with the above adverse events are outlined in Section 5.

- Dose escalation will proceed within each cohort according to the following scheme. Dose-limiting toxicity (DLT) is defined above.

Number of Patients with DLT at a Given Dose Level	Escalation Decision Rule
0 out of 3	Enter 3 patients at the next dose level.
$\geq 2$	Dose escalation will be stopped. This dose level will be declared the maximally administered dose (highest dose administered). Three (3) additional patients will be entered at the next lowest dose level if only 3 patients were treated previously at that dose. If $\geq 2$ initial patients experience a DLT at dose level 1, de-escalation to dose level -1 will occur.
1 out of 3	Enter at least 3 more patients at this dose level. 
 
• If 0 of these 3 patients experience DLT, proceed to the next dose level.
 
• If 1 or more of this group suffer DLT, then dose escalation is stopped, and this dose is declared the maximally administered dose. Three (3) additional patients will be entered at the next lowest dose level if only 3 patients were treated previously at that dose.
 

$\leq 1$ out of 6 at highest dose level below the maximally administered dose	This is generally the recommended phase 2 dose. At least 6 patients must be entered at the recommended phase 2 dose.

#### 4.3 General Concomitant Medication and Supportive Care Guidelines

Because there is a potential for interaction of AZD6244 and Capecitabine with other concomitantly administered drugs through the cytochrome P450 system, the case report form must capture the concurrent use of all other drugs, over-the-counter medications, or alternative therapies. The Principal Investigator should be alerted if the patient is taking any agent known to affect or with the potential to affect selected CYP450 isoenzymes (2C9 and 1A2).

- Investigators should document the patient's comedications to investigate any potential drug interactions.
- Because there is a potential for interaction of AZD6244 with other concomitantly administered drugs through the cytochrome P1A2 system, the case report form (CRF) must capture the concurrent use of all other drugs, over-the-counter medications, or alternative therapies. Throughout the study, patients should avoid changes to, or the addition of all concomitant medications, in particular any that may affect the metabolism of AZD6244 (eg, CYP1A2 or 3A4 inhibitors/inducers), unless considered clinically indicated. If patients are taking strong inducers or inhibitors of CYP1A2 these medications will be discontinued prior to initiation of protocol therapy.
- Because there is a potential for interaction of Capecitabine with other concomitantly administered drugs through the CYP2C9 system, the case report form (CRF) must capture the concurrent use of all other drugs, over-the-counter

medications, or alternative therapies. The Principal Investigator should be alerted if the patient is taking any agent known to affect or with the potential to interact with Capecitabine. Patients will be transitioned to an acceptable alternative if available. Common examples include aluminum and magnesium hydroxide containing antacids, coumadin, and phenytoin.

- Diarrhea will be managed with the following regimen: loperamide (4 mg PO) at onset of symptoms, followed by 2 mg loperamide every 2 hours while awake (or 4 mg PO every 4 hours while sleeping) up to a maximum of 16 mg loperamide per day. Additional agents may be used concurrently if loperamide is not adequate to control diarrhea as a single agent.
- The use of white cell growth factors is discouraged during the course of radiation but is allowed for management of neutropenia at physician discretion in concordance with ASCO guidelines.
- Nausea and vomiting will be managed through the use of appropriate simple supportive measures (*e.g.*, prochlorperazine). To date, 5 HT3 antagonists have not been routinely required but allowed if necessary.
- Patients will receive full supportive care as needed while on this study including blood product support, intravenous hydration, antibiotic treatment and treatment of other newly diagnosed or concurrent medical conditions.
- Patients should be advised to drink plenty of water or take rehydration fluids to avoid dehydration if diarrhea occurs.

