## 5.0 DOSING DELAYS/DOSE MODIFICATIONS

### 5.1 AZD6244

AZD6244 dose reductions will occur in the event of a DLT. In the event of a DLT that is an overlapping toxicity with Capecitabine, AZD6244 will be dose reduced. If a Capecitabine associated toxicities occur following discontinuation of AZD6244, Capecitabine dose adjustments will occur as deemed appropriate by the Principal Investigator in conjunction with the participating Medical Oncology Associate Investigator. AZD6244 dose reductions will not occur for established non-DLT Capecitabine toxicities (e.g. Grade 2 hand-foot syndrome).

Dose de-escalation will occur as described in the table below for DLT's and the following overlapping toxicities

- **Grade  $\geq 3$  diarrhea that persists despite appropriate medical management including anti-diarrheal medications**
- **Grade  $\geq 3$  nausea and vomiting that persists despite appropriate medical management including anti-nausea medications**
- **Grade 2 hand foot that persists despite interruption of capecitabine**

Dose De-Escalation Schedule			
Dose Level	Dose		
	AZD6244	Capecitabine	Radiation*
Level -1	50 mg PO QD Weeks 1-7	825 mg/m  PO every 12 hours Weeks 2-7	5040 cGy Weeks 2-7
Level 1	50 mg PO BID Weeks 1-7	825 mg/m  PO every 12 hours Weeks 2-7	5040 cGy Weeks 2-7
Level 2	75 mg PO BID Weeks 1-7	825 mg/m  PO every 12 hours Weeks 2-7	5040 cGy Weeks 2-7
* An additional 360 cGy may be delivered for fixed T4 tumors for a total dose of 5400 cGy			

Diarrhea must be managed symptomatically. IV hydration and use of loperamide, as well as close observation, are recommended for diarrhea if clinically indicated. C If control takes

longer than 2 days, medical evaluation including relevant diagnostic procedures, alternative treatment, and possible investigation of DPD deficiency should be considered. Capecitabine and AZD6244 may be held for up to 72 hours and will not be re-started until diarrhea has resolved to grade  $\leq 1$ . In patients with grade 3 diarrhea evaluation for C. difficile colitis should be considered. Patients with neutropenia and diarrhea should be considered for empiric use of prophylactic antibiotics such as oral quinolones.

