## APPENDIX C

### MEDICATIONS THAT MAY CAUSE QTc PROLONGATION

The following table presents a list of drugs that may prolong the QTc. These drugs are prohibited during the study. AZD 6244 may be administered after a 5 half-life washout period elapses following the use of these drugs. Washout period is based on roughly 5 half-lives and rounded to a convenient interval.

Compound	Compound Half Life	Possible Washout Period - Hours	Possible Washout Period - Days
Alfuzocin	~10 hours		7
Amantadine	17 +/- 4 hours (10-25)		4
Amiodarone (cordarone)	58 days (15-142) 36 days (active metabolite)		180
Amitriptyline*	> 24 hours, wide interpatient variability		
Arsenic trioxide	Not characterized		
Azithromycin	40 hours		
Bepidil	42 hr (26-64)		10
Chloral hydrate	Readily converted to Trichloroethanol (active metabolite T 1/2 =7-10 hour)	48	
Chloroquine	Prolonged (days to weeks)		
Chlorpromazine	30 +/- 7 hours		7
Cisapride	6 – 12 hour, up to 20 hour	60	
Clarithromycin	Non linear PK3-4 hr (250mg Q12) 5-7 hr (500mg Q12)	36	
Cloroquine	6 to 60 days; mean 20 days		
Desipramine*	> 24 hours, wide interpatient variability		
Disopyramide	6.7 hr (4-10)	36	
Dofetilide	10 hr	48	
Dolesetron	8.1 hr		
Domperidone	7-8 hr	48	
Doxepin*	> 24 hours, wide interpatient variability		
Droperidol	2.2 hours	10	
Erythromycin	* Each salt form has different Half life*		
Felbamate	20-23 hr		5
Flecainide	20 hr (12-27)		5
Foscarnet	87.5+/-41.8 hours *distribution and release from bone*		20
Fosphenytoin	12-29 hr		6
Gatifloxacin	7-14 hr	48	
Gemifloxacin	7 hours	48	
Grepafloxacin	16 hr		3
Halofantrine	6-10 days ( variable among individual)		45
Haloperidol	18 +/-5 hr		5
Ibutilide	6 hours (2-12) * variable among subject*	36	
Imipramine*	> 24 hours, wide interpatient variability		
Indapamide	14 hours (biphasic elimination)		3
Isradipine	8 hours ( multiple metabolites)	48	
Levofloxacin	6-8 hours	48	
Levomethadyl	Multiple compartment PK with active metabolite 2.6 day for LAAM, 2 day for nor-LAAM, 4 day for dinor-LAAM		20
Lithium	24 hour (10-50)		7

Compound	Compound Half Life	Possible Washout Period - Hours	Possible Washout Period - Days
Mesoridazine	24-48 hours ( animal study)		10
Methadone	15-30 hours		7
Moexipril/HCTZ	2-9 hour (include active metabolite) for moexipril; 5.6-14.8 hours for HCTZ	48	
Moxifloxacin	12 +/-1.3 hours	72	
Naratriptan	6 hours	36	
Nicardipine	~ 2 hour post IV infusion	12	
Nortriptyline*	> 24 hours, wide interpatient variability		
Octreotide	1.7 hours	12	

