Ofloxacin	5 to 7.5 hours		2
Ondansetron	4 hours (IV/IM); 3 hours (PO)		1 to 3
Pentamidine	6.4+/-1.3 hours	36	
Pimozide	55 hours		10
Procainamide	3-4 hour for PA and NAPA (active metabolite)	24	
Protiptyline*	> 24 hours, wide interpatient variability		
Quetiapine	6 hours	36	
Quinidine	6-8 hours in adult; 3-4 hours in children	36	
Quinine	4-5 hours		
Risperidone	3-20 hours (extensive to poor metabolizer) 9-hydroxyrisperidone (active metabolite) T $\frac{1}{2}$ =21-30 hours (extensive to poor metabolizer)		4
Salmeterol	5.5 hours ( only one datum)	36	
Sotalol	12 hours	72	
Sparfloxacin	20 hours (16-30)		4
Sumatriptan	2.5 hours	12	
Tacrolimus	~34 hours in healthy; ~19 hours in Kidney transplant		7
Tamoxifen	5-7 days (biphasic)		30
Telithromycin	2-3 hr	24	
Thioridazine	20-40 hours (Phenothiazines)		7
Tizanidine	2.5 hours	12	
Vardenafil	4 to 5 hours		
Venlafaxine	5 +/-2 hours for parent comp. 11+/-2 hours for OVD (active metabolite)	60	
Voriconazole	6 hours; dose dependent		
Ziprasidone	7 hr	36	
Zolmitriptan	2.8-3.7 hours (higher in female)	18	

\* Weakly associated with Torsades de Pointes and/or QT prolongation but that are unlikely to be a risk for Torsades de Pointes when used in usual recommended dosages and in patients without other risk factors (e.g., concomitant QT prolonging drugs, bradycardia, electrolyte disturbances, congenital long QT syndrome, concomitant drugs that inhibit metabolism).

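### Sections 4.3 and 5.1 permit 5-HT3 antagonists and oral quinolones as classes without pointing to Appendix C, which prohibits nine named members of those classes on study

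*Combined protocol and SAP*

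**What the plan says.** Four places in the combined protocol and SAP bear on this.

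- **Section 4.3 (supportive care).** Nausea and vomiting are managed first with simple measures; prochlorperazine is the example given. The section then adds: "To date, 5 HT3 antagonists have not been routinely required but allowed if necessary". It also carries a general caution that "patients should avoid changes to, or the addition of all concomitant medications", with particular attention to drugs affecting AZD6244 metabolism. That caution gives way where a drug is judged clinically indicated.
- **Section 5.1 (dose modification, diarrhea text).** "Patients with neutropenia and diarrhea should be considered for empiric use of prophylactic antibiotics such as oral quinolones".
- **Appendix C.** It tabulates drugs that may prolong the QTc and states: "These drugs are prohibited during the study". It continues: "AZD 6244 may be administered after a 5 half-life washout period elapses following the use of these drugs".
- **Exclusion criterion 3.2.8.** Patients who need a QT-prolonging medication are not eligible, and the reader is sent to Appendix C. Apart from the table of contents, this is the only reference to that appendix.

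**The concern.** Sections 4.3 and 5.1 are what a clinician will open when a patient is vomiting, or is neutropenic with diarrhea. Both give permission by drug class, and neither mentions QT or sends the reader to the list of prohibited drugs. The one cross-reference is in the eligibility criteria, which are applied before treatment starts.

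The patients concerned are those for whom QT matters most on the protocol's own terms. Criterion 3.2.7 treats uncorrectable hypokalemia as a QT risk factor, and the Appendix C footnote adds electrolyte disturbances and concomitant QT-prolonging drugs. Vomiting and diarrhea are common routes to electrolyte loss. Section 6.2.1.1 records QTc prolongation and hypokalemia on AZD6244 trials, with the relationship to the drug undetermined. At stake is avoidable exposure to a drug that the sponsor has already decided patients should not receive during the study.

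**Working it through.** No sample size, power or error rate is involved. The check is a count and a side-by-side reading.

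**Step 1: count the Appendix C entries in each class.**

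| Class | Text that permits it | Entries prohibited in Appendix C | Count |
|---|---|---|---|
| 5-HT3 antagonists | Section 4.3 | ondansetron; dolasetron (entered as Dolesetron) | 2 |
| Quinolones | Section 5.1 | gatifloxacin, gemifloxacin, grepafloxacin, levofloxacin, moxifloxacin, ofloxacin, sparfloxacin | 7 |

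Total: 2 + 7 = 9. Quinine and the chloroquine entries are left out because they are not quinolone antibiotics. None of the nine carries the asterisk that Appendix C uses for drugs only weakly associated with QT prolongation.

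**Step 2: can both texts be obeyed?** Yes, by choosing an unlisted member of the class. The prohibition covers named drugs, not whole classes. But the permitting sentences do not tell the reader that a choice has to be made, and the documents name no permitted agent in either class.

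**Step 3: does the caution in 4.3 close the gap?** No. It is directed mainly at drug metabolism, and it yields when a drug is clinically indicated. A needed anti-emetic or antibiotic would meet that test. The exception qualifies only its own sentence and does not lift the Appendix C ban, but it does not direct anyone to that ban either.

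**Step 4: would monitoring catch it?** The Study Calendar (Section 10) schedules EKGs pre-study, on Day 1, on Day 8 and in week 4, and adds one for a cardiorespiratory adverse event. Section 4.1.1 asks for an EKG after edema, cardiac symptoms or respiratory events. Treatment runs to week 7. Starting an Appendix C drug is not among the triggers, and no EKG is scheduled after week 4. Serum chemistry in weeks 1 to 9 includes potassium and calcium but not magnesium. Concurrent medications are reviewed in weeks 1 to 7, and the team meets weekly (Section 6.8.1). Weekly review may find a listed drug only after it has been given.

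**Step 5: how often would this arise?** The documents do not say. They show only that these sections will be used. About half of patients with nausea events on AZD6244 needed medication (Section 2.1.2.2). Grade 3 or higher diarrhea may reach 20% with capecitabine in this setting (Section 2.2). Grade 3 or 4 neutrophil decrease on single-agent capecitabine is 2.4% (Section 6.2.1.2). None of these is a rate of listed-drug use, so none is converted into one here.

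**The case against.** The strongest reply is that the protocol already handles this. Appendix C is unconditional, and a specific ban limits a general permission. Section 4.3 offers 5-HT3 antagonists only as a second line after prochlorperazine, which is not listed. Section 5.1 says only that quinolones should be considered, and gives them as an example. Criterion 3.2.7 excludes patients with QTc above 470 msec and other QT risks, a screening EKG is required, and at most 18 patients are planned. All of this is correct, and it keeps the matter small. It does not put the ban in front of the person who is prescribing.

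Three stronger readings are tempting, and the documents do not support them.

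- **That the sections flatly contradict Appendix C.** They do not; unlisted agents satisfy both.
- **That AZD6244 must be held for the washout period if a listed drug is given, at a calculable cost in dose.** The washout sentence can refer to use before entry or to use on study, and the table heads its columns as possible washout periods. The listed washouts for these agents run from 1 to 4 days, with none shown for dolasetron. A figure built on them alone would leave out the days spent taking the listed drug, which the documents do not give. Comparison with Section 5.1, where "Capecitabine and AZD6244 may be held for up to 72 hours", fails for the same reason, and that hold is for diarrhea. A mandatory hold could also reduce dose intensity in a trial whose aim is the MTD of continuous dosing.
- **That DLT counts or escalation would be distorted.** Section 13.1 requires a DLT to be attributable to the study treatment, and nothing in the documents shows such an effect.

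**Conclusion.** The point holds as a partial inconsistency between current sections. Two supportive-care provisions permit drug classes that contain nine agents prohibited on study, with no cross-reference at the point of use. Its size is that count of nine; frequency and clinical consequence cannot be estimated from the documents. The conclusion rests on reading the Appendix C prohibition as covering the whole study, which is what its wording says, and on assigning the nine drugs to their classes, since the table does not label them. It is a minor safety correction that should be made. It changes no statistical quantity, and no effect on DLT scoring or dose escalation is shown.

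**What to change.** - In Section 4.3, after the permission for 5-HT3 antagonists, add: *except agents listed in Appendix C*.
- In Section 5.1, after the mention of oral quinolones, add the same words.
- Alternatively, name the permitted unlisted agents in both places. The sponsor would have to choose them.
- Separately, state whether the Appendix C washout applies to a listed drug given during the study and, if so, what happens to AZD6244 dosing. That choice is the sponsor's.

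The added words require no procedures and no patients. The cost is a narrower choice of anti-emetic and antibiotic, which Appendix C already imposes. Prochlorperazine, the anti-emetic named in Section 4.3, remains available. No change to the DLT definition is needed.
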